#### 5.4.5. Clinical laboratory evaluation at baseline

Serum creatinine and eGFR locally analyzed at Visit 2 and Visit 4 will be described as baseline characteristics using the Safety Set. These parameters will be described as quantitative variables in both Standard International (SI) and conventional (i.e. United States) units. Numbers and percentages of subjects with a value of eGFR < 60 mL/min/1.73m^2 will also be presented.

Serum creatinine and eGFR locally analyzed at Visit 1 will be only listed.

Hematology and biochemistry parameters centrally analyzed before the 1st injection of contrast agent will be presented as part of safety analysis (see Section 5.6.4) along with those collected after. Urinalysis data will be listed only.

The tables and the listing that will be displayed are detailed in Sections 6.1.1.4 and 6.2.4 respectively.

#### **5.4.6. Vital signs, physical findings and other observations related to safety at baseline**

ECG and vital signs data measured before the 1st injection of contrast agent will be presented as part of safety analysis (see Section 5.6.5).

### 5.4.7. Prior therapies

Previous medications are medications ended before the first administration of contrast agent. They correspond to medications with the category of end period: 1 = "Before first IMP administration".

Subject's previous medications will be coded using the World Health Organization (WHO) Drug dictionary version B3 WHO DDE Sept 2017. The number and percentage of subjects who took concomitant medications ended before the first administration of contrast agent will be summarized according to Anatomical Therapeutic Chemical (ATC) system main group (ATC1, ATC first level corresponds to the first letter of the ATC code).

The table will be sorted according to the percentage of subjects reporting at least one previous medication from the most to the least frequent globally.

The tables and the listing that will be displayed are detailed in Sections 6.1.1.4 and 6.2.4 respectively.

CONFIDENTIAL	FORM  STATISTICAL ANALYSIS PLAN N° GDX-44-004  VERSION 1.0      DATED: 09JAN2018	
--------------	--	--

#### 5.4.8. Other baseline characteristics

Other baseline characteristics collected are subject intolerance to contrast agent history, physical examination, pregnancy test and MRI examination.

#### 5.4.8.1 Subject Intolerance to Contrast Agent History

Subject intolerance to contrast agent history at screening includes the following parameters:

- Previous intolerance due to contrast agent: Yes; No.
- If yes, Type of product (multiple choices): Gadolinium complex; Iodinated contrast agent; Barium; Diagnostic radiopharmaceutical; Other.

These data will be displayed in a listing only (see Section 6.2.4).

#### 5.4.8.2 Physical Examination

These data will be displayed in a listing only (see Section 6.2.4).

### 5.4.8.3 *Pregnancy Test*

These data will be displayed in a listing only (see Section 6.2.4).

#### 5.4.8.4 MRI Examination

MRI examination at Visit 2 and Visit 4 includes the following parameters:

- MRI performed: Yes; No.
- If yes:
  - Time between the injection of contrast agent and T1 post-injection sequence (minutes) calculated for each of the MRI procedure using the following formula: Date/time of the T1 post-injection - Date/time of the injection of contrast agent.
  - MRI examination: Brain; Spine.
  - Magnetic field strength: 1.5 Tesla (T); 3.0T. Any other value will be considered as missing.

Descriptive statistics for MRI examination will be presented by contrast agent using the FAS. The occurrence of any deviation from the MRI procedures (Yes; No; If yes, Specification (multiple choices): Scanner-related deviation; Subject-related deviation) and the anatomy, that is to say the MRI examination as per central readers, will be only listed.

The table and the listing that will be displayed are detailed in Sections 6.1.1.5 and 6.2.5 respectively.

CONFIDENTIAL	FORM	
STATISTICAL ANALYSIS PLAN N° GDX-44-004		Page 29 / 60
VERSION 1.0      DATED: 09JAN2018		

## 5.5. Efficacy evaluation

Listing of all efficacy data will be presented in CSR appendix 16.2.6.

### 5.5.1. Primary analysis of the primary criteria

The primary objective of the study is to determine a safe and effective dose of P03277 based on a comparison of CNR between several doses, 0.025, 0.05, 0.1 and 0.2 mmol/kg of P03277 and MultiHance® at 0.1 mmol/kg.

The primary criterion is the CNR calculated from the SI measurement of maximum 3 enhanced lesions by the 3 independent blinded readers. CNR averaged for matching lesions per subject will be used in the primary analysis.

The primary analysis will test differences of means of primary criterion for each dose of P03277 compared to MultiHance® and will be done for each of the 3 independent blinded readers (off-site) using the PPS. Holm's step-down method [1] will be used to address multiplicity testing considering the 4 contrast agents to be tested.

A subject will be analyzed as soon as he has a matching evaluation of the CNR at both MRIs by at least one off-site reader. Therefore the numbers of subjects analyzed by reader may be different.

### 5.5.1.1 Statistical Hypothesis for the Primary Analysis

For each of the 3 readers and each dose of P03277 (4 doses), a mixed model for correlated data will be done for assessing the primary criterion. Factors included in the 12 different models are contrast agent (P03277 and MultiHance®) and the pre contrast CNR measurement (baseline).

Differences between means for each contrast agent *versus* MultiHance® will be tested according to the following items:

- $\mu_i$  is the expected average of CNR of enhanced lesions for each dose of P03277 (where  $i$  is corresponding to one dose of P03277).
- $\mu_0$  is the expected average of CNR of enhanced lesions for corresponding MultiHance® group.

### Null hypothesis

$$H_i: \mu_i - \mu_0 \leq 0, i = 1 \dots 4$$

### Alternative hypothesis

$$K_i: \mu_i - \mu_0 > 0, i = 1 \dots 4$$

For each contrast agent, the p-value for comparing the doses of P03277 with corresponding MultiHance® is calculated for testing above hypotheses and the associated 95% two-sided Confidence Interval (CI) is provided.

### 5.5.1.2 Holm's Step-Down Method

Let  $p_1, p_2, p_3$  and  $p_4$  be the ordered p-values (from the lower to the upper value) and  $H_1, H_2, H_3$  and  $H_4$  be the corresponding ordered null hypothesis. The testing procedure starts with the most significant comparison and

CONFIDENTIAL	FORM	
	STATISTICAL ANALYSIS PLAN N° GDX-44-004	
	VERSION 1.0      DATED: 09JAN2018	Page 30 / 60

continues as long as tests are significant (meaning that the alternative statistics is met). The procedure stops the first time a non-significant comparison occurs and all remaining hypotheses will not be tested.

In the first step,  $H_1$  is rejected if  $p_1 \leq \alpha/4$ , in the second step (if any)  $H_2$  is rejected if  $p_2 \leq \alpha/3$ , in the third step (if any),  $H_3$  is rejected if  $p_3 \leq \alpha/2$  and in the fourth and last step,  $H_4$  is rejected if  $p_4 \leq \alpha$ , with  $\alpha$  being the one-sided significance level of 0.025.

The models will include the contrast agent group, the period and the unenhanced value as baseline data. The parameters of the mixed models will be estimated using the SAS® procedure Mixed. The difference between contrast agent groups in mean score and associated 95% two-sided CI will be computed.

### 5.5.1.3 SAS® Procedure

The SAS® procedure used for the primary analysis of the primary criterion will be the following:

```
proc mixed data = XXX method = REML;
  class subject trt period;
  model eval = trt period baseline;
  random subject / type = cs;
  lsmeans trt / pdiff = controlu('MultiHance') tdiff cl alpha = 0.025;
  /* The following code is needed as previous statement lsmeans does not provide the upper limit of CI */
  lsmeans trt;
  estimate "P03277 - MultiHance" trt 1 -1 /cl;
run;
```

A plot of Least Squares (LS) means from the mixed models for correlated data will be designed. The figure will display the doses on X axis and the difference *versus* MultiHance® on Y axis

#### 5.5.1.4 Validation of Statistical Model

The validation of the statistical model used for the primary analysis will be done through graphical method. A normal Quantile-Quantile (Q-Q) plot will be drawn for each off-site reader. If we observe visually a strong deviation from normality hypotheses, alternative methods can be proposed to fit more appropriately the data distribution (log transformation, non-parametric analyses, ...).

### 5.5.1.5 Selection Basis for Clinical Dose

The clinical dose will be selected according to the clinical benefit/risk ratio among the four doses evaluated based on the primary and secondary efficacy criteria analyzed in this study. A dose of P03277 which is not proved to be superior to the comparator on the primary criterion could however be recommended for use.

The table and the figures that will be displayed are detailed in Section 6.1.2.1.1 and the listings in Section 6.2.6.1.

CONFIDENTIAL	FORM	
STATISTICAL ANALYSIS PLAN N° GDX-44-004		Page 31 / 60
VERSION 1.0      DATED: 09JAN2018		

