P03277 is a Gd chelate with a very high stability, limiting the risk of release of toxic free Gd in the body. The results of preclinical data indicate a good tolerance and a low toxicity profile at dose levels and exposure much higher than the anticipated clinical dose. This satisfactory tolerance has been confirmed in a phase I study in a total of 54 healthy volunteers. No serious adverse events occurred in any of these volunteers at any of tested dose at 0.025, 0.5, 0.75, 0.1, 0.2, and 0.3 mmol/kg BW. No clinically significant changes in vital signs or laboratory findings were noted.

The ability of P03277 to be a MR contrast agent has been demonstrated by at least two-fold higher T1 relaxivity compared to other available GBCAs. A proof of concept has been obtained for the efficacy of P03277 as a MR contrast agent for CNS imaging in a model of brain tumor (C6 glioma) implanted in rats. In this experimental brain tumor model, the dose of 0.1 mmol/kg of P03277 allowed for an increase in contrast enhancement of at least 30% as compared to other GBCAs administered at dose of 0.1 mmol/kg, including MultiHance® (highest relaxivity).

The purpose of the study is mainly to determine the effective and safe clinical dose of P03277 injection to be recommended as the further P03277 approved dose for phase III studies, by comparing with approved GBCA for CNS indication (here MultiHance®, current commercial product with the highest relaxivity) using a cross-over design (allowing intra-subject comparison to evaluate the study primary criterion). This dose selection will be based on the superiority of P03277 in term of efficacy (based on CNR criterion) towards MultiHance® in subjects with CNS indication.

 CONFIDENTIAL	Protocol No. GDX-44-004 Version No. 2.0 (Protocol including amendment n°1) Date: 11 July , 2016	 Page 22 / 84
---------------------------------------------------------------------------------------------------	----------------------------------------------------------------------------------------------------------	-----------------------------------------------------------------------------------------------------

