#### Selection basis for clinical dose:

The effective clinical P03277 doses will be the doses for which at least 2 out of the 3 off-site blinded readers meet the alternative hypothesis for the primary endpoint.

If more than one effective clinical dose is identified based on the primary statistical analysis described above, then the clinical target dose will be selected according to the clinical benefit/risk ratio for each of them including the efficacy secondary criteria analyzed in this study.

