## 1. SUMMARY OF THE STUDY PROTOCOL

This document presents the Statistical Analysis Plan (SAP) for Guerbet, Protocol No. GDX-44-004: "P03277 Dose Finding Study in Central Nervous System (CNS) Magnetic Resonance Imaging (MRI)".

This analysis plan is based on the protocol Version 2.0 including amendment n°1 dated 11 July 2016.

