#### 4. CHANGES IN THE CONDUCT OF THE STUDY OR PLANNED ANALYSES

The protocol was amended on one occurrence. See amended protocol for a full list of changes.

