#### RATIONALE FOR ANY DEVIATION FROM PRE-SPECIFIED ANALYSIS PLAN PERFORMED

It was planned in the protocol to repeat on the PPS the evaluation of secondary efficacy criteria in case of a difference from the FAS by more than 15%. It has been decided that only the analyses of data from off-site readings for some relevant secondary criteria will be repeated on the PPS.

Further, three secondary criteria have been added since the last amendment: The Contrast-to-Noise Ratio calculated based on the noise issued from the CerebroSpinal Fluid (CSF): CNRCSF, the Lesion-to-Brain Ratio (LBR) and the Contrast enhancement percentage. The three criteria are calculated by subject, and by independent blinded reader in a centralized procedure (off-site readers) and the result is provided by exam for each reader by averaging the parameter for maximum 3 enhanced lesions.

$\text{CNR}_{\text{CSF}}$  is derived for each lesion, from the SI measurement, according to the following formula:

$$\text{CNR}_{\text{csf}} = \frac{SI_{\text{lesion}} - SI_{\text{ht}}}{SD_{\text{noise}}}$$

where  $SJ_{lesion}$  = the SJ in the ROJ in the lesion.

$SI_{bt}$  = the SI in the ROI in the lesion.

SDnoise ≡ SD of CSF noise

LBR is derived for each lesion, from the SI measurement, according to the following formula:

$$\text{LBR} = \frac{SIlesion}{SIht}$$

where  $SJ_{lesion}$  = the SJ in the ROI in the lesion.

$SI_{ht}$  = the SI in the ROI in the lesion.

Contrast enhancement percentage is derived for each lesion, from the SI measurement, according to the following formula:

$$\text{Contrast Enhancement Percentage} = \frac{SI_{post} - SI_{pre}}{SI_{pre}}$$

where  $SI_{post}$  = the SI in the ROI in the lesion post contrast media administration.  
 $SI_{pre}$  = the SI in the ROI in the lesion pre contrast media administration.

These three criteria will be analyzed as the primary criterion.

CONFIDENTIAL	FORM	
STATISTICAL ANALYSIS PLAN N° GDX-44-004		Page 18 / 60
VERSION 1.0      DATED: 09JAN2018		

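### The SAP drops the protocol's 2-of-3-reader test for an effective dose, allows a dose not shown superior to be recommended, and does not declare the change

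*SAP*

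**What the plan says.** Protocol section 12.3 (selection basis for the clinical dose) has two steps. Effective doses are those for which "at least 2 out of the 3 off-site blinded readers meet the alternative hypothesis for the primary endpoint". Benefit/risk, with the secondary efficacy criteria, comes second and is conditional: "If more than one effective clinical dose is identified based on the primary statistical analysis described above". Protocol section 1 gives the same basis: "This dose selection will be based on the superiority of P03277 in term of efficacy (based on CNR criterion) towards MultiHance".

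SAP section 5.5.1.5 has one step. The dose is to be "selected according to the clinical benefit/risk ratio among the four doses evaluated based on the primary and secondary efficacy criteria", and the section adds: "A dose of P03277 which is not proved to be superior to the comparator on the primary criterion could however be recommended for use". It has no reader-agreement rule.

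On provenance, SAP section 1 says "This analysis plan is based on the protocol Version 2.0 including amendment n°1 dated 11 July 2016". SAP section 4 says "The protocol was amended on one occurrence. See amended protocol for a full list of changes". Its own list of departures covers a reduced repeat of secondary analyses on the per-protocol set (PPS) and the fact that "three secondary criteria have been added since the last amendment". Dose selection is not mentioned.

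**The concern.** The primary objective in both documents is to find a safe and effective dose from the CNR comparison with MultiHance. If the two documents turn the same test results into different answers, the objective has no single pre-specified answer.

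Two things are at stake. First, a dose could be put forward although it fails the protocol's definition of effective, and the SAP does not say whether that recommendation or the test result answers the primary objective. Second, the primary analysis consists of 12 separate models (three readers by four doses), and the SAP accepts that the subjects analysed may differ by reader. Without a rule for combining readers, the status of a dose on which they disagree is not fixed before the blind is broken.

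**Working it through.** **1. The two rules side by side**

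| Element | Protocol 12.3 | SAP 5.5.1.5 |
|---|---|---|
| Definition of an effective dose | At least 2 of 3 readers reject | None given |
| Doses open to selection | Those that pass | All four |
| Role of benefit/risk | Second step, if more than one dose passes | The whole rule |
| Dose not shown superior | Outside the effective set | May be recommended |
| No dose passes | Not addressed | Recommendation still possible |

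The tests themselves are the same in both documents: Holm within each reader over four doses, one-sided α = 0.025, thresholds 0.00625, 0.00833, 0.0125 and 0.025. The pooled three-reader model (SAP 5.5.2.2) is supportive, so it does not supply the missing rule.

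**2. Is the change declared?** SAP section 4 sends the reader to the amended protocol. That is Version 2.0, the version on which the SAP says it is based and the one that contains the 2-of-3 rule. The pointer leads back to the omitted text.

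**3. The plan's own figure.** The 50 evaluable subjects per group cannot be reproduced, because the mean MultiHance CNR is not given. With n = 50, SD 3.01 and 90% power, the noncentral t gives these detectable differences:
- one-sided 0.025: 1.41 (paired) or 1.97 (two-sample);
- one-sided 0.00625: 1.66 or 2.31.

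Read as a 30% increase, these imply a MultiHance mean from 1.41/0.30 = 4.7 to 2.31/0.30 = 7.7. Neither document says which level the 90% refers to. The finding does not depend on this, but the power ranges in step 5 do.

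**4. How much the reader rule matters when no dose is superior.** Assumptions: doses independent (parallel groups), normal test statistics, and a common correlation ρ between readers, which the documents do not give. The table shows the probability that at least one dose is rejected by the stated number of readers (5 million simulated trials per ρ).

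| ρ | Any one reader | 2 of 3 | All three |
|---|---|---|---|
| 0 | 0.0724 | 0.00046 | 0.000001 |
| 0.3 | 0.0698 | 0.0030 | 0.0001 |
| 0.5 | 0.0658 | 0.0067 | 0.0007 |
| 0.7 | 0.0584 | 0.0125 | 0.0027 |
| 0.9 | 0.0446 | 0.0203 | 0.0093 |
| 1.0 | 0.0248 | 0.0248 | 0.0248 |

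Closed-form checks:
- independent, any one: 1 − (1 − 0.00625)^12 = 0.0725;
- independent, 2 of 3: about 4 × 3 × 0.00625² = 0.00047;
- independent, all three: 4 × 0.00625³ = 0.000001;
- identical readers: 1 − (1 − 0.00625)^4 = 0.0248.

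Under any dependence, the 2-of-3 rule is bounded by 3 × 0.025/2 = 0.0375.

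**5. A truly superior dose.**

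*Case A: 90% power per reader at the Holm step.* Power to pass 2 of 3 is 0.90 for identical readers and 3 × 0.9² × 0.1 + 0.9³ = 0.972 for independent readers. The floor under any dependence is 1 − 1.5 × 0.1 = 0.85.

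*Case B: 90% computed at 0.025.* At the first Holm step (0.00625), per-reader power is 0.759 (paired, df 49, noncentrality 3.307) or 0.765 (two-sample, df 98, noncentrality 3.274). Power to pass 2 of 3 is then 0.76 for identical readers, about 0.85 to 0.86 for independent readers, with a floor of about 0.64. At later Holm steps, per-reader power rises to between 0.79 and 0.90.

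Readers split when one or two of the three reject. For independent readers:
- power 0.90: 1 − 0.9³ − 0.1³ = 0.270;
- power 0.76: 1 − 0.76³ − 0.24³ = 0.547.

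By simulation, the split probabilities at ρ = 0.5 are 0.203 (power 0.90) and 0.380 (power 0.76). At ρ = 0.9 they are 0.094 and 0.168, and for identical readers they are zero.

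**The case against.** The strongest reply is that little of the inference changes. The per-reader Holm tests, the 0.025 level and the 95% confidence intervals all stay, so anyone can apply the 2-of-3 rule to the planned output. This is a phase IIb dose-finding study, and the protocol itself leaves the final choice among effective doses to benefit/risk. It has no sentence forbidding recommendation of a dose outside the effective set and no rule for the case where none passes. Effective and recommended are also different words, and the SAP is open that such a dose would not have been shown superior.

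Much of this is fair. The conflict concerns the decision rule, not the tests or the sample size. The one-reader and three-reader rules appear in neither document; they only bracket what an undefined term could mean. Under the SAP every dose is eligible anyway, so a reader split decides whether a dose counts as shown superior, not whether it may be recommended. The SAP's section 6 pages and table attachments could not be read, so the absence of a reader rule is established for the readable text only.

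The reply does not remove the conflict. The protocol defines the effective doses, and its rationale ties selection to superiority; the SAP follows neither and does not say so. Being able to apply a rule afterwards is not the same as committing to it beforehand.

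**Conclusion.** The concern holds and should be resolved before the blind is broken. The protocol gates selection on a defined test result, the SAP removes that gate without declaring it, and followed literally the two can answer the primary objective differently from the same data.

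Under the protocol rule, the chance of calling any dose effective when none is superior runs from 0.0005 to 0.025 across the correlations considered, and cannot exceed 0.0375. Those figures describe the protocol rule only; the chance that the SAP route recommends a particular dose cannot be computed, because the recommendation need not follow from a test. What can be sized is the ambiguity in the SAP's notion of superiority: at ρ = 0.5, the null probability differs about tenfold between adjacent reader rules. For a superior dose, readers split in 9% to 27% of trials at per-reader power 0.90 and in 17% to 55% at 0.76, for correlations from 0.9 down to 0. All of these rest on an assumed reader correlation. The textual conflict needs no such assumption.

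**What to change.** Reconcile SAP 5.5.1.5 with protocol 12.3 before the blind is broken.

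1. State the primary CNR conclusion for each dose by the protocol's definition: effective only if at least two of three readers reject its null hypothesis at its Holm step in the PPS primary analysis. Say that the pooled model in 5.5.2.2 is supportive only.
2. If no dose meets the definition, report that CNR superiority was not shown.
3. If the sponsor wishes to keep the option of recommending a dose outside that set, declare and justify it in SAP section 4, and label the recommendation as lying outside the confirmatory test, with the per-reader results and planned confidence intervals beside it.

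This takes no position on which dose or which clinical selection rule is right. The cost is SAP wording, with no new data or analysis. The sponsor gives up some freedom to present a dose not shown superior as the study's primary conclusion.

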### 5.5.2. Supportive analyses of primary criterion

### 5.5.2.1 FAS Analysis

The primary analysis will be repeated using the FAS. However, this analysis will be restricted to subjects with CNR data at both MRIs. It will avoid the mixed model to impute any missing CNR data. All lesions will be considered, including not matched lesions, on the contrary to the primary analysis. Lesions not matching between both MRIs will therefore be included in this supportive analysis.

The table and the figure that will be displayed are detailed in Section 6.1.2.1.2.

